7.5 Extent of Exposure

The extent of exposure to belatacept will be summarized in two different ways: by total number of active infusions and by length of exposure.

A frequency distribution table will be presented summarizing the total number of active infusions administered in the ranges of 5 infusions for the belatacept treatment group.

In addition, the length of exposure to the assigned treatment will be summarized and presented according to the following time intervals (in days): ≤ 28 (≤ 1 month), 29-84 (2-3 months), 85-168 (4-6 months), 169-252 (7-9 months), 253-364 (10-12 months), 365-448 (13-15 months), 449-532 (16-18 months), 533-616 (19-21 months), 617-728 (22-24 months), ≥ 729 (> 24 months). This summary will also be produced for the TAC treatment group. The number of subjects in each category will be displayed.

For belatacept, the length of exposure will be calculated as the last infusion date + 28 days or death date (if earlier) minus first infusion date.

For TAC, the length of exposure will be calculated as the last infusion dose + 10 days or death date (if earlier) minus first dose date.

All summaries of exposure (both for total number of infusions and length of exposure) will also include a summary of the mean, the standard deviation, the median and the maximum and minimum values (i.e. range).

These analyses will be produced using the as treated population.

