7.7 Safety

Safety analysis will be based on all randomized, transplanted, and treated subjects (as treated population). All AEs will be summarized and listed by treatment groups. SAEs and AEs that result in discontinuation of the study drug will also be tabulated in detail. Laboratory marked abnormalities that are determined as “critically” out of range per the central laboratory manual, will be summarized descriptively. There will be no statistical testing of group differences with respect to frequencies of adverse events or laboratory marked abnormalities or changes in clinical laboratory tests from baseline (last measurement prior to first dose date/time).

All safety summaries except those for reports of death, graft loss, PTLD, malignancies, and serious infections, will be based only on data available at each of the scheduled analysis time points, applying ‘last dose date + 56’ cut counting rules. For events of death, graft loss, PTLD, malignancies, and serious infections, two different summaries will be prepared. The first summary will be based only on data available applying ‘last dose date + 56’ cut counting rules. The second summary will be based on all available data without applying ‘last dose date + 56’ cut counting rules.

The frequencies and exposure adjusted incidence rates using person-year method will be summarized by treatment regimen groups and overall.

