7.7.1.2 Events of Special Interest

The following adverse events of special interest, as obtained from the additional CRF pages or appropriate source documentation will be listed or both listed and summarized by treatment group, as specified below:

- Serious Infections (listing and summary).
- PTLD (listing).
- PML (listing).

- Malignancies (other than PTLD) including non-melanoma skin carcinomas (listing).
- TB Infections (serious and non-serious) (listing).
- CNS Infections (serious and non-serious) (listing).
- Viral Infections (serious) (listing and summary).
- Infusion related reactions within 24 hours since belatacept infusion (listing and summary).

The conventions for counting adverse events are provided in [Section 8.8](#). Listings of all adverse events will also be based on all available data up to database lock.

Incidence rates will be calculated for SAEs and AEs of clinical interest for the Month 24 analysis. The numerator is the number of subjects having the first occurrence of the event within the period specified. The denominator is the overall total exposure in years (total exposure days/365.25) within the period specified. However, for these summaries subjects experiencing the event of interest will have their exposure censored at the time of the first occurrence of the event. The resulting incidence rate is multiplied by 100 to express the rate per 100 person-year of exposure. Subjects for whom the time of onset of the first occurrence of the AE of interest is in a given interval will not be included in the exposure and incidence rates in later intervals.

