APPENDIX 3 LIST OF PERI-INFUSIONAL EVENTS

List of peri-infusional events (infusion related reactions) is obtained from the preferred terms that correspond to the BMS predefined list of MedDRA preferred terms (Infusion -related reactions-EU- SMQ_CODE BMS03061). The peri-infusional events are those occurring within 24 hours of Belatacept administration. The latest MedDRA Version of the list of events at the time of the database lock will be used.

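### The SAP's only incidence-rate rule for events of special interest suits infusion related reactions poorly: for a belatacept completer, about 96% of its denominator is time when the event cannot occur

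*SAP*

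**What the plan says.** SAP 7.7.1.2 puts infusion related reactions on its list of events of special interest and promises them both a listing and a summary by treatment group. SAP Appendix 3 fixes the window: "The peri-infusional events are those occurring within 24 hours of Belatacept administration".

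The same section then gives a single rate rule. Its scope is: "Incidence rates will be calculated for SAEs and AEs of clinical interest for the Month 24 analysis". On the numerator: "The numerator is the number of subjects having the first occurrence of the event within the period specified". On the denominator: "The denominator is the overall total exposure in years (total exposure days/365.25) within the period specified". Follow-up after an event is removed: "subjects experiencing the event of interest will have their exposure censored at the time of the first occurrence of the event". SAP 7.7.1.1 also stops exposure for AE and SAE rates at 56 days after the last dose.

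SAP 7.7 sets the columns: "The frequencies and exposure adjusted incidence rates using person-year method will be summarized by treatment regimen groups and overall".

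Nothing in the SAP exempts infusion reactions from this rule or gives a per-infusion denominator. SAP 7.5 does already count infusions in the belatacept group: "A frequency distribution table will be presented summarizing the total number of active infusions administered".

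**The concern.** A person-year rate is informative when a subject is at risk throughout the time counted. Here the subject is at risk, by definition, for one day after each infusion. Everything else in the denominator is time in which the event cannot be recorded. The resulting rate moves with how long subjects stay on belatacept and how closely their infusions are spaced, even when the risk at each infusion is unchanged.

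The overall column raises a separate problem. It would pool in the tacrolimus group, whose members receive no belatacept and contribute only zero-risk time to the rate and zero-risk subjects to the percentage.

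The incidence of events of special interest is a listed secondary endpoint (SAP 4.2). What is at stake is how clearly the report describes infusion tolerability.

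**Working it through.** The documents state no infusion-reaction rate or at-risk time, so there is no planned figure to reproduce. The check compares exposure days with at-risk days.

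**1. Number of infusions.** Protocol Table 5.1-4 gives Day 1 and Weeks 1, 2, 4, 8 and 12 (6), then Weeks 16, 20 and 24 (3). Table 5.1-5 gives every 4 weeks from Week 28 to Week 104 (20). Total: 6 + 3 + 20 = 29, hence at most 29 at-risk days.

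**2. Exposure of a completer.** Under Protocol 5.3.2, Week 4 is Day 29, so Week 104 is Day 729, which is 728 days after Day 1. The last belatacept infusion is taken as the last dose.
- Last dose + 56 days (SAP 7.7.1.1): 728 + 56 = 784 days (785 if both end days are counted); 784/29 = 27.0.
- Last infusion + 28 days (the length-of-exposure rule in SAP 7.5): 756/29 = 26.1.
- Day 1 to Day 728 window (SAP 8.4): 728/28 = 26.0 without the Day 729 infusion, or 728/29 = 25.1 with it.

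The time not at risk is 1 − 29/784 = 96.3% on the first reading and 1 − 29/728 = 96.0% on the last.

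**3. Subjects who stop early (last dose + 56 days).** One infusion: 56/1 = 56. Two infusions (Day 7): 62/2 = 31. Stop at Week 4: 84/4 = 21. Stop at Week 12: 140/6 = 23.3. Stop at Week 24: 224/9 = 24.9.

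**4. Same risk per infusion, different rates.** Assume a 1% risk at every infusion and, for simplicity, ignore censoring at the first event. The rate per 100 person-years is then (infusions × 365.25)/(exposure days):
- one infusion only: 365.25/56 = 6.5
- stop at Week 4: 4 × 365.25/84 = 17.4
- completer: 29 × 365.25/784 = 13.5

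**5. Effect of the columns.** Assume 35 subjects per group, all completers except that x belatacept subjects react at the first infusion and are censored there at one day. Belatacept exposure is (35 − x) × 784 + x days. The overall column adds 35 × 784 = 27,440 tacrolimus days. Infusions counted are (35 − x) × 29 + x.

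| x | % of belatacept | % overall | per 100 PY, belatacept | per 100 PY, overall | first reactions per 100 infusions |
|---|---|---|---|---|---|
| 1 | 2.9 | 1.4 | 1.37 | 0.68 | 0.10 |
| 2 | 5.7 | 2.9 | 2.82 | 1.37 | 0.21 |
| 4 | 11.4 | 5.7 | 6.01 | 2.82 | 0.44 |
| 7 | 20.0 | 10.0 | 11.64 | 5.18 | 0.86 |

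For x = 4: belatacept exposure is 31 × 784 + 4 = 24,308 days = 66.6 years, and 400/66.6 = 6.0. Overall exposure is 51,748 days = 141.7 years, and 400/141.7 = 2.8. Infusions are 31 × 29 + 4 = 903, and 400/903 = 0.44.

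Censoring at the event barely changes the belatacept ratio (26.5 to 27.0 for 1 to 7 reactors at the first or the fifteenth infusion). In the overall column the ratio of exposure days to at-risk days is about 54 to 60.

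**The case against.** The strongest reply is that the SAP never plainly promises this rate. Infusion reactions are given a listing and a summary by treatment group. The rate rule covers SAEs and an undefined class of AEs of clinical interest, and five of the eight listed events get a listing only, so the rule cannot cover every listed event automatically. The overall column comes only from the general sentence in SAP 7.7. SAP 8.7 also refers to sponsor safety conventions that are not part of these documents. This stands as a caution: applying the rule here is an inference. It is still the most natural one. Only three listed events get a summary, and the other two (serious infections and serious viral infections) are already SAEs. Among the summarized events, infusion reactions are therefore the only one that the extra class can add.

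A reader might infer that infusion risk goes unmeasured. The documents do not support that. SAP 7.7 requires frequencies as well as rates, SAP 7.7.1.1 uses number and percent for AE summaries, and safety is reported in the as-treated population, which requires a dose of belatacept or tacrolimus. The belatacept column therefore gives a valid per-subject risk, and there is a listing.

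A reader might also infer that the denominator is all time on study, or that reactions will look 27 times rarer than they are. Neither follows. Exposure stops at the first event and at last dose + 56 days. The ratio compares amounts of time and is not a bias in an estimate: a 1% risk per infusion gives a completer rate of 13.5 per 100 person-years, a larger number than 1 per 100 infusions.

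Finally, a pooled per-infusion rate has its own weakness. With 4 of 35 subjects reacting at the first infusion, it reads 0.44 per 100. This point stands, and it is why the first infusion needs its own line.

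**Conclusion.** The point holds for the person-year rate and the overall column only. If the rule is applied to infusion related reactions, about 96% of a belatacept completer's denominator is time not at risk (a ratio of about 25 to 27 across readings of exposure, and 21 to 56 for the early stopping times checked). The rate then mixes time on treatment and dosing frequency with risk per infusion. The overall column adds subjects who cannot have the event, which roughly halves both the percentage and the rate.

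The figures assume the full protocol schedule, one at-risk day per infusion, the last belatacept infusion as the last dose, and 35 subjects per group. The 1% risk and the numbers of reactors are illustrations, not figures from the documents.

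The consequence is limited to descriptive safety reporting. The study plans no statistical tests (SAP 7.2), and no primary result depends on this rate. It is a low-cost improvement worth making.

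**What to change.** In SAP 7.7.1.2, state that the person-year rule and the overall column do not apply to infusion related reactions. For belatacept-infused subjects only, report:
- the number and percent with at least one reaction;
- the number of reactions per 100 infusions, with the first infusion shown separately, because a pooled per-infusion rate would hide reactions concentrated there.

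A split by dosing phase is optional. With 35 subjects, the listing may be enough for that. It would also help to say which events count as AEs of clinical interest, so that the scope of the rate rule is clear.

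The cost is a short addition to the SAP text and one extra table shell. The infusion counts are already derived for SAP 7.5, and Protocol Tables 5.1-2 and 5.1-3 already require contact within 48 hours of every belatacept infusion to ask about events in the first 24 hours. No new data collection is needed.

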7.7.1.3 Multiple Adverse Events

Descriptive summaries of adverse events that takes into account the number of times that an AE was reported by individual patient, will be provided. In order to prepare these summaries, the AE data will be processed according to standard BMS algorithms to categorize each line of patient data as a new occurrence or a continuation of an existing event. This determination will be based upon onset and resolution dates. All continuations of an existing event will be collapsed into a unique AE record. Each line of patient AE data will represent a unique AE record and will contain the earliest onset day, the latest resolution day (if available), highest intensity, treatment ever required, the maximum severity observed, the last known assessed relationship to study medication by the investigator as well as highest action taken in the order of (highest to lowest): drug discontinued, drug interrupted, dose reduced, dose increase, and none.

This data will be presented as the rate per 100 years of patient exposure. Exposure to study medication will be calculated according to approved standard BMS algorithms as well.

As an example, if 10 patients report 8 unique episodes of headache and had a combined cumulative exposure of 40 years to study medication, the incidence rate is reported as $8/40*(100)$ or 20 cases per 100 patient years of exposure.

The summary information will be tabulated for:

- The total number and incidence rate (exposure adjusted) of occurrences for all AEs occurring in at least 5% of the subjects in Safety population (defined in [Section 6.2](#))
- All AEs and SAEs:

- the total number of events and incidence rate (exposure adjusted) at every 6-month time intervals.
- the number of subjects experiencing an AE once or more than once (analysis to be produced only for AEs).

A listing of all unique AE records will be also provided.

EudraCT Summaries:

Exposure adjusted event summaries including multiple occurrences of unique adverse events for EudraCT reporting requirements will be presented by treatment. These summaries include serious adverse events, drug related serious adverse events and non-serious adverse events using a global cutoff of 5 percent.

7.7.2 Laboratory Test Analysis

Laboratory marked abnormalities as identified using pre-defined criteria (see [APPENDIX 4](#)), will be descriptively summarized with frequency and percentage. All laboratory values of a laboratory analyte will be listed for subjects with at least one marked abnormality for this parameter will be listed (independent of study period).

All available laboratory parameters included in the Hematology and Chemistry Panels in protocol Section 5.3.6.1 will also be summarized over time (with mean, SD, median, minimum, Q25, Q75, and maximum).

7.7.3 Other Safety Considerations

Vital Signs

Body temperature (in degrees Celsius [°C]) and Heart rate (beats per minute) will be summarized by treatment (with mean, SD, median, minimum, Q25, Q75 and maximum) at protocol-specified intervals. The same analysis conventions will be followed as those for systolic and diastolic blood pressure (see [Section 7.6.2.5](#)).

Viral Loads and Immunoglobulins

Summaries over time will be provided by treatment group for BK, CMV and EBV viral loads and Serum levels of IgG and IgG subclasses post-transplants.

[Redacted]

[Redacted]

[Redacted]

[Redacted]

[Redacted]

[Redacted]

[Redacted]

[Redacted]

[REDACTED]

[REDACTED]

[REDACTED]

[REDACTED]

[REDACTED]

[REDACTED]

[REDACTED]

[REDACTED]

8 CONVENTIONS

The conventions to be followed in the computation of summary measures of efficacy and safety endpoints are described in this section.

[REDACTED]

8.2 Analysis Period of Interest

All analyses will be produced for the 24 month-treatment period, unless specified otherwise in the sections above. For these analyses focusing at month 6 and month 12, the analyses conventions in [Section 8.4](#) will be followed.

8.3 Missing Data Handling

The following conventions will be followed while handling missing data. Only the relevant endpoints along with the specifics of the convention are included in this section.

Subject Survival and Graft Survival

Any subject (either randomized to belatacept or CNI) with unknown subject and graft survival status at Month 12 or Month 24, that is, whose last known follow-up date occurred prior to Day 334 or Day 698, respectively, will be considered as having experienced an event of graft loss or death, if at least one of the following criteria have been met during their documented period of follow-up post-randomization:

- Subject experienced at least one episode of BPAR at the time of, or prior to the last follow-up date.
- Subject was diagnosed as having PTLD at the time of, or prior to the last follow-up date.
- Subject's reason for discontinuation of study medication was lack of efficacy.
- A diagnosis of biopsy confirmed Polyomavirus associated nephropathy was reported as an adverse event before discontinuation.
- Subject's last calculated GFR (4-variable MDRD equation) was $< 15\text{mL}/\text{min}/1.73\text{m}^2$.

The remaining subjects with unknown patient and/or graft survival status at Months 12 or 24 (those who do not meet any of the above criteria) will be considered missing and not be included in the analyses or listing of the death and graft loss. For example, a patient with unknown status of the graft function and patient survival, and with no records of the above mentioned criteria, will not be considered in the numerator or denominator, while computing the percentage of death or graft loss.

Acute Rejection

Any acute rejection-free subject who is not followed-up through the entire event-counting period due to any reason will be considered as having no acute rejection during that period.

Renal Function

Missing cGFR values due to death or graft loss will be imputed with value of 0 and all other missing values will remain missing.

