 - c) Subject and allograft survival rates among those subjects who did and those who did not experience CSBPAR. This analysis will be produced only if there are at least 5 subjects across treatment groups who died or experienced graft loss during the 24 month-treatment period.
- 5) Analysis of the composite endpoints of CSBPAR, death, or graft loss will be produced only if there is at least one CSBPAR and at least one death or graft loss. These analyses will include the proportion of all subjects who experience CSBPAR, death, or graft loss at 12 and 24 months and a time to event analysis of the composite endpoint of CSBPAR, death, or graft loss.
- 6) All safety analyses will only be produced for the whole 24 Month treatment period. The corresponding safety analyses at 6 and 12 months will not be produced.
- 7) Analysis of immunogenicity: The protocol specifies summaries of titers of detectable anti-belatacept antibodies at Weeks 8, 12, and 24 post study termination (subjects who discontinue belatacept only). Instead of descriptive statistics, a listing will be provided for all positive subjects. Similarly, the analysis of descriptive statistics for titers of detectable anti-belatacept antibody will not be produced.

- 8) Analysis of any clinical consequences of CSBPAR (and associated changes in the expression of exploratory gene sets associated with acute rejection) at 6, 12 and 24 months post-transplant will be presented as follow:
 - a) The extent to which renal function recovered to the pre-rejection baseline will include the serum creatinine values related to CSBPAR in the corresponding listing.
 - b) The percentage of subjects who, post-CSBPAR, are reported to have developed infection or malignancy will not be summarized. Instead, a listing will be provided.
 - c) The percentage of subjects with, and titers of detectable, de novo (post-transplant) anti-belatacept antibodies will not be summarized. Instead, this information will be included in a listing of immunogenicity results with corresponding belatacept concentrations and selected laboratory parameters and events of special interest.
 - d) The subject and graft survival rates among those subjects who did, and those who did not experience CSBPAR will be provided only if there are at least 5 subjects across treatment groups who died or experienced graft loss during the 24 month-treatment period.

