7.6.2 Secondary Endpoints

7.6.2.1 Subject and Graft Survival

A listing will be provided of all subjects who died or experienced graft loss at any time during the study. A listing of all subjects with unknown subject and graft survival status at the end of the 24 month-treatment period will be provided.

If there are at least 5 subjects across treatment groups who died or experienced graft loss during the 24 month-treatment period, the following analyses will be produced:

- The composite endpoints of patient and graft survival at 24 months respectively will be summarized within each treatment groups, using point estimates of the proportion of subjects surviving with a functioning graft, and the corresponding 95% CIs. The point estimate and its 95% CIs will also be generated for the difference between the two treatment regimens.
- The proportion of subjects who die, proportion of subjects who have a graft loss, and the proportion of subjects who experience the following outcomes will each be summarized using point estimates and 95% CI within each treatment group.
 - Overall graft loss rates at 24 months.
 - Rates of death with a functioning graft at 24 months.

- Rates of pure (death-censored) graft loss at 24 months.
- In addition, Kaplan-Meier (KM) estimates of cumulative subject and graft survival rates will also be summarized.
- The subject and allograft survival rates will be summarized among those subjects who did and those who did not experience CSBP. This analysis will be produced only if there are at least 5 subjects across treatment groups who died or experienced graft loss during the 24 month-treatment period.

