8.9 Missing, Unknown or Partial Dates

No imputation of event dates will be performed on any efficacy endpoints, including acute rejection, graft loss, death, laboratory measures and blood pressures, with the exception of cases wherein the onset date of an episode related to acute rejection is unknown; in such cases, the date of the first biopsy for that episode will be used as the onset date of the episode.

Missing Start Dates of study therapy

No date imputation will be done for missing start dates of study therapy.

Missing Start Dates of concomitant medications

If start date is missing then it will be imputed differently depending on whether the consent date is available or not. If the consent date is available then the start date will be imputed by the consent date. Otherwise, the start date will be imputed as 01 January 1900.

Partial Start Dates of concomitant medications

If a partial start date is available then it will be imputed by the earliest possible date based on the partial start date. For instance, if the available partial start date is Year 2005, then the imputed start date will be 01 January 2005. However, if the available partial start date is May 2005, then the imputed start date will be 01 May 2005.

Missing or Continuing Stop Dates of concomitant medications

If a stop date is missing or treatment is continuing then it will be imputed as 31 December 2099.

Partial Stop Dates of concomitant medications

If a partial stop date is available then it will be imputed by the latest possible date based on the partial stop date. For instance, if the available partial stop date is Year 2005, then the imputed stop date will be 31 December 2005. However, if the available partial stop date is May 2005, then the imputed stop date will be 31 May 2005.

Missing or Partial Onset Dates of Adverse Events

Before imputing any missing or partial onset dates, two new dates will be defined: a surrogate date for each onset date (missing or partial), and an earliest possible date (EPD) for each partial onset date. The surrogate date will be defined as the first non-missing valid date from the following list (in order of precedence):

- First active study medication date of any study medication,
- informed consent date, or
- visit date corresponding to the visit at which the event was reported if a valid non-missing date is not available for any of these dates, the surrogate date will be set to missing.

[figure not shown]

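### The survival summary by CSBPAR status is partly circular, because the SAP's rule for unknown status uses a prior rejection to assign the outcome

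*SAP*

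**What the plan says.** SAP 8.3 treats status as unknown for a subject "whose last known follow-up date occurred prior to Day 334 or Day 698" (Month 12 and Month 24 respectively). Such a subject "will be considered as having experienced an event of graft loss or death, if at least one of the following criteria have been met". The five criteria are a prior BPAR ("Subject experienced at least one episode of BPAR at the time of, or prior to the last follow-up date"), PTLD, stopping study medication for lack of efficacy, biopsy-confirmed polyomavirus nephropathy, and a last calculated GFR below 15. Every other subject of unknown status "will be considered missing and not be included in the analyses or listing of the death and graft loss"; the worked example in the same section says that such a subject "will not be considered in the numerator or denominator".

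SAP 7.6.2.1 plans this summary: "The subject and allograft survival rates will be summarized among those subjects who did and those who did not experience CSBP" (CSBP here is the SAP's short form of CSBPAR). SAP 7.1 keeps it in items 4c and 8d. It is produced only if at least 5 subjects across the arms die or lose the graft over 24 months. Item 3e removes the landmark summaries by earlier rejection, but not this one. No text exempts it from 8.3, and no version without the imputation is planned.

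On dates, SAP 8.9 states: "No imputation of event dates will be performed on any efficacy endpoints, including acute rejection, graft loss, death". Its one exception concerns the onset of a rejection episode. SAP 7.2 and Table 7.2-1 plan Kaplan-Meier estimates and a Cox hazard ratio for time to death or graft loss, under the same 5-subject condition.

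**The concern.** The by-CSBPAR summary is meant to show whether subjects with a rejection fare worse. Under 8.3 a lost subject with CSBPAR is always scored as a failure, because CSBPAR is biopsy proven and so meets the BPAR criterion. A lost subject without rejection is usually removed. The acute rejection rule in 8.3 also classes a rejection-free subject with incomplete follow-up as having had no rejection, so the removals fall mainly on the non-CSBPAR group. Equal loss to follow-up in the two groups therefore produces worse apparent survival after rejection, even when rejection has no effect.

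A second, separate gap is that an event assigned by status has no date. The SAP does not say whether such a subject is dated, censored or left out in the time-to-event analyses, so those results can differ from the proportions for reasons that a reader cannot trace.

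**Working it through.** **The plan's own figures.** The documents give no figure for unknown status or for survival by CSBPAR. The only checkable figures nearby are the precision statements in SAP 5 at 35 per arm, and they reproduce: 0.21% to 16.37% for a 3.8% rate, 0.09% to 15.14% for 3%, and -13.17% to 11.32% for the difference. None is in dispute. They matter here only because the assumed 6-month rates imply few rejections: 35 × 0.038 + 35 × 0.03 = 2.38 subjects.

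**Inputs (all assumptions).** Let e be the true risk of death or graft loss and L the share with unknown status. Both are the same with and without CSBPAR, and loss is unrelated to outcome. Let q be the share of lost non-CSBPAR subjects who meet another criterion. Ranges: e 3-10%, L 5-20%, q 0-25%.

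**Formulas under 8.3.**
- With CSBPAR: (1 - L)e + L.
- Without CSBPAR: [(1 - L)e + Lq] / [(1 - L) + Lq].

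Example with e = 5%, L = 10%, q = 10%:
- With CSBPAR: 0.90 × 0.05 + 0.10 = 14.5%.
- Without: (0.045 + 0.010) / (0.90 + 0.010) = 0.055 / 0.910 = 6.0%.

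| e | L | q | With CSBPAR | Without | Difference (points) | Ratio |
|---|---|---|---|---|---|---|
| 3% | 10% | 0 | 12.7% | 3.0% | 9.7 | 4.2 |
| 3% | 10% | 10% | 12.7% | 4.1% | 8.6 | 3.1 |
| 3% | 10% | 25% | 12.7% | 5.6% | 7.1 | 2.3 |
| 5% | 5% | 10% | 9.8% | 5.5% | 4.3 | 1.8 |
| 5% | 10% | 10% | 14.5% | 6.0% | 8.5 | 2.4 |
| 5% | 20% | 10% | 24.0% | 7.3% | 16.7 | 3.3 |
| 10% | 5% | 25% | 14.5% | 11.2% | 3.3 | 1.3 |
| 3% | 20% | 0 | 22.4% | 3.0% | 19.4 | 7.5 |

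The last two rows are the extremes of the grid. The true difference is zero in every row.

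**Same inputs, one rule for both groups.** With observed status only, both rates equal e (5.0% against 5.0%). With every unknown counted as an event, both equal (1 - L)e + L (14.5% against 14.5% at e = 5%, L = 10%). Either way the artefact disappears, so it comes from the asymmetry and not from imputation as such.

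**Small numbers.** With 3 CSBPAR subjects, one lost and two alive with a functioning graft, the rule reports 1/3 (33%); observed status gives 0/2. With 7 and one lost it reports 1/7 (14%) instead of 0/6.

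**Dates.** SAP 7.2 censors an event-free subject who discontinues early at last follow-up. SAP 8.3 says that the imputed subject is not event-free. SAP 8.9 supplies no date. The three sections together do not settle how that subject enters the Kaplan-Meier or Cox analysis.

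**The case against.** The strongest reply is that little may turn on this.

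- **The threshold.** At e = 3%, 70 subjects give 70 × 0.03 = 2.1 expected events, and the binomial chance of 5 or more is about 6%; at 5% it is about 27%. In the low-risk rows, where the ratios are largest, the table would probably not be produced. This stands, with one reservation: the SAP does not say whether imputed events count towards the 5, so the rule could help trigger the table.
- **Few lost subjects.** Protocol 3.5 and 3.6 seek survival status for everyone to Month 24 whatever happens to treatment, and 3.6.1 and 3.6.2 allow public records and third-party tracing. At 2.38 expected rejections and 10% lost, about 0.24 subjects would be imputed. The 2.38 covers 6 months only and the summary runs to 24, but no later rate is given.
- **Transparency.** Nothing is tested (SAP 7.2), and 7.6.2.1 lists subjects of unknown status, so a careful reader could probably find the affected cases.
- **BPAR may be broader than CSBPAR.** The SAP only expands the abbreviation. If borderline or not clinically suspected findings count, some non-CSBPAR subjects are imputed too. That narrows the asymmetry without removing it.

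Three stronger readings are tempting, and the documents do not support them:

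- A reader might infer that the between-arm comparison is biased against the arm with more rejection. That comparison is not circular. The rule carries an arm difference in BPAR among lost subjects into survival, but whether that is bias depends on their true outcomes, which are not given.
- A reader might infer that imputed events cannot enter the Kaplan-Meier analysis, so that it must disagree with the proportions. SAP 8.9 bars imputing dates; it is silent on events assigned by status. The handling is undefined, and the results can differ but need not.
- A reader might take a four-fold ratio as the expected distortion. It needs e = 3%, L = 10% and q = 0, and is one cell of a wide grid.

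**Conclusion.** The point holds for the by-CSBPAR survival summary. Its grouping variable is also a trigger for its outcome, and nothing in the SAP exempts it. Known outcomes are untouched, and the summary is descriptive and conditional on at least 5 deaths or graft losses. If there is no true association and loss is unrelated to outcome, the built-in difference is about 3 to 19 percentage points (ratio about 1.3 to 7.5) over the assumed ranges, always against CSBPAR. The size depends on a loss rate that the documents do not state. With only a handful of rejections, one lost subject can dominate the rate. The missing convention for imputed events in the time-to-event analyses is a real but lesser gap. None of this shows that 8.3 is wrong for the overall or between-arm proportions, where a conservative composite is a defensible trade-off.

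**What to change.** 1. In SAP 7.6.2.1 and 7.1 items 4c and 8d, state that the by-CSBPAR summary uses observed deaths and graft losses only, by Kaplan-Meier with censoring at last contact, and that the 8.3 imputation does not apply to it.
2. Keep 8.3 for the overall and between-arm proportions.
3. State one convention for 8.3 events in the Kaplan-Meier and Cox analyses. If they are dated at last follow-up, amend 8.9 to allow it.
4. State whether imputed events count towards the 5-event threshold.

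The cost is SAP wording: no new data, and Kaplan-Meier survival is already planned. The price is that the by-CSBPAR summary gives up the conservative scoring of lost subjects with rejection and relies on loss being uninformative. Those subjects stay visible in the planned listing of unknown status.
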